5.1.5 Manufacturer

DSM Nutritional Products Europe Ltd, Switzerland.

5.1.6 Dosage and Administration

A dose is one tablet (30 mg genistein) per oral daily. Subjects or parents/guardians will be instructed to bring in unused pills to study visits. For children who are unable to swallow tablets, instructions for crushing and administering will be given to a caregiver (Procedure Manual). Tablets may be crushed and delivered via feeding tube only if subjects are unable to take the medication orally and the feeding tube terminates in the stomach. Delivery to the duodenum or jejunum may alter genistein pharmacokinetics.

Refer to the Procedure Manual for additional administration instructions and [Section 4.7.4](#) for dose modification instructions.

5.1.7 Expected Adverse Events

The side effects of usage of genistein reported in the literature are mild. The most common effect is abdominal pain (≤ grade 2). This is the only AE that will be considered to be expected for the purposes of this study.

Genistein may have estrogenic properties. Therefore any condition which might be worsened by estrogen, such as breast cancer, uterine cancer, ovarian cancer, endometriosis or uterine fibroids, may also be worsened by administration of genistein. The effect of genistein in someone who is pregnant or breast-feeding is not known.

5.2 Placebo

5.2.1 Formulation

The formulation includes: microcrystalline cellulose, dicalcium phosphate, and magnesium stearate in a ratio of 10:20:1. Tablets will weigh about 300 mg.

5.2.2 Manufacturer

DSM Nutritional Products Europe Ltd, Switzerland.

5.2.3 Dosage and Administration

Subjects will take one tablet per oral daily. Tablets are approximately 260 mg of placebo (cellulose).

Refer to the Procedure Manual for additional administration instructions and [Section 4.7.4](#) for dose modification instructions.

5.2.4 Expected Adverse Events

None.

5.3 Clinical Supplies/Study Supplement Ordering

Genistein and placebo tablets will be provided to the Core Investigational Pharmacy by DSM Nutritional Products. The Core Investigational Pharmacy will supply each site with full bottles of 100 tablets to be dispensed in smaller quantities as defined in the Procedure Manual based upon cycle length. Site pharmacies must distribute the study supplement in accordance to institutional and state regulations.

Undispensed clinical supplies, including missed doses, must be returned to the Core Investigational Pharmacy. Bottles must not be transferred from one subject to another subject or from one protocol to another protocol.

Details regarding study supplement ordering are provided in the Procedure Manual.

5.4 Storage and Stability

The study supplement may be stored for up to 36 months from the date of manufacture at < 25 °C. Keep container tightly closed. See the Procedure Manual for directives should a temperature excursion occur.

5.5 Agent Accountability

Subject Pill Diaries must be collected and study medication reconciled at the end of each cycle. Record agent accountability on the Investigational Agent Accountability Record. Both forms are located in the Procedure Manual appendices.

Each site will be responsible for providing periodic study supplement reconciliation reports to the Study Manager.

DRAFT

6 EVALUATIONS AND ASSESSMENTS

6.1 Study Procedures and Assessments Table

Table 3: Schedule of Events

Assessment ¹	Pre-Treatment	Treatment Phase				Follow-up ²
	Day -28 to Day 1 ³	Cycle 1 Day 1 ^{3,4}	Cycles 1 - 4 Weekly ⁵	Cycles 2 - 4 Day 1	Cycle 4 Last Day ⁶	
Informed Consent	X					
Eligibility Determination	X					
Baseline ⁷ and Demographic ⁸ Data	X					
Randomization ⁹	X					
Medical History/Baseline Condition	X					
Physical Exam ¹⁰	X	X	X	X		
Height and Weight		X		X		
Chemistry/Metabolic Panel ¹¹	X	X		X		
CBC with Differential ¹²	X		X	X		
CRP, ESR, and Homocysteine ¹³	X			X	X	
Cytokine and Isoflavone Panels ¹⁴		X		X	X	
Audiogram ¹⁵	X			X	X	
Concomitant Medications Review ¹⁶	X ¹⁷	X	X	X	X	
Adverse Events Review		X	X	X	X	X
Study Medication Dispensing		X		X		
Subject Pill Diary ¹⁸		X	X	X	X	
Study Medication Reconciliation				X	X	

¹ All visits and assessments must be completed within ± 72 hours of the milestone date unless otherwise specified.

² Subjects must be followed for 30 days following the last study intervention for AEs and for 6 months for SAEs, unless consent is withdrawn.

³ Cycles begin on Day 1. There is no Day 0.

⁴ Cycle 1 Day 1 assessments do not need to be repeated if completed in the 7 days prior (i.e. Day -7 to Day 1) unless otherwise stated.

⁵ Weekly visits are to occur at 7-day intervals between Day 1 and the cycle's last day.

⁶ The last day of a cycle corresponds to the Day 1 of the next cycle. The last day's number will vary by cycle length.

⁷ Diagnosis, stage, grade, site(s) of disease, anti-neoplastic treatment +/- radiation regimen

⁸ Age, sex, race, and ethnicity

⁹ Randomization must occur within the 2 days prior to the anticipated Cycle 1 Day 1. ([Section 4.5](#))

¹⁰ Full physical exam at the beginning of each cycle of chemotherapy, and a symptom-directed physical exam at each of the weekly treatment visits. Collect height, weight and BSA on Day 1 of each cycle.

¹¹ Chemistry labs to assess for general safety must be conducted on Day 1 of each cycle. They must include serum creatinine, total bilirubin, AST, and ALT.

¹² CBC must be collected once during Baseline (Day -7 to 1), and then Day 1 of Cycles 2, 3, and 4, and Day 8 of Cycles 1, 2, 3, and 4. Once ANC begins to decrease each cycle, obtain twice a week until ANC recovery (see [Section 7.1](#) for definition of ANC recovery). CBC must include the following: hemoglobin, hematocrit, platelet count, total white blood cell count and automated differential (manual differential if automated not available).

¹³ Blood sample must be drawn at Baseline (Day -7 to Day 1), Day 1 of Cycles 2, 3, and 4, and the last day of Cycle 4.

¹⁴ Blood sample must be drawn on Day 1 of Cycles 1, 2, 3, and 4, and the last day of Cycle 4.

¹⁵ In subjects receiving platinum based chemotherapy only, an audiogram must be resulted at baseline (Day -7 to Day 1) and again 0 - 4 days prior to Day 1 of Cycles 2, 3, 4, and the last day of Cycle 4. If hearing loss is detected then adjust dose per [Section 4.7.4](#).

¹⁶ G-CSF, antimicrobials, blood product transfusions, anti-neoplastic agents, and soy-based products ([Section 4.8](#) and [6.4](#))

¹⁷ Concomitant medications used in the 28 days prior to the initiation of the study intervention

¹⁸ Dispense Day 1 of each cycle. Weekly review recommended but not required. Collect and review on the last day of each cycle.

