Both genistein and placebo tablets will be provided by DSM Nutritional Products Europe Ltd, Switzerland.

Other study intervention(s): The chemotherapeutic regimen for each subject will be determined by the treating physician and must contain a combination of at least two agents from the following list during each of the four cycles administered in this study: actinomycin, carboplatin, cisplatin, cyclophosphamide, daunorubicin, doxorubicin, etoposide, ifosfamide, topotecan.

Criteria for evaluation (i.e. endpoints):

Efficacy: To evaluate the effectiveness of genistein administration during myelosuppressive chemotherapy, the following endpoints will be compared between genistein cycles and placebo cycles:

Primary endpoint:

- Duration of grade 4 neutropenia, defined as an absolute neutrophil count (ANC) of < 500 cells/ μ l

Secondary endpoints (per cycle):

- Severity of neutropenia
- Duration of grade 4 neutropenia during hospital admissions for febrile neutropenia
- Frequency and duration of unplanned hospital admissions due to (an) adverse event(s)
- Days with fever (temperature > 101.5° F, or > 100° F more than once in a 24-hour period)
- Incidence and severity of infections
- Duration of antimicrobial agent use
- Duration and severity of oral mucositis
- Duration and severity of peripheral motor neuropathy (in subjects receiving vincristine)
- Incidence and severity of hearing impairment and tinnitus (in subjects receiving a platinum-based chemotherapy agent)
- Number of days delayed and percent reduction of full, planned doses of anti-neoplastic agents due to (an) adverse event(s)
- Incidence of primary and secondary G-CSF use
- Number of required blood product transfusions
- Cytokine, growth factor, C-reactive protein, and homocysteine levels as well as erythrocyte sedimentation rates

Safety: Safety will be assessed by incidence and severity of AEs and changes in physical examinations.

Statistical methods:

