6.3 Treatment Phase Assessments (Cycles 1 – 4)

Investigators should maintain good clinical practice and perform standard of care assessments and procedures per local institutional guidelines. In addition, the following list of study-specific assessments must be performed once a patient enters the Treatment Phase. All visits and assessments must be completed within \pm 72 hours of the milestone date unless otherwise specified.

- The following will be performed for the purposes of assessing clinically significant AEs. AEs found prior to the first study supplement dose must be reported as baseline conditions. See [Section 9](#) and the Procedure Manual for more information about AE reporting.
 - Chemistry/metabolic liver function labs on Day 1 of each cycle: must include serum creatinine, total bilirubin, AST, and ALT (Procedure Manual)
 - CBC with differential on Day 1 of Cycles 2, 3, and 4, and at weekly visits: must include hemoglobin, hematocrit, platelet count, total white blood cell count and automated white blood cell differential (manual differential if automated not available) (Procedure Manual). See below for additional requirements for ANC reporting.
 - Full physical exam on Day 1 of each cycle and a symptom-directed physical exam at each of the weekly visits ([Section 6.2.1](#))
 - The Pre-treatment and Cycle 1 Day 1 physical exams may be combined performed \leq 72 hrs. prior to Cycle 1 Day 1.
 - Subjects receiving vincristine must be assessed for vincristine toxicity in the form of peripheral motor neuropathy.
 - Audiograms for subjects receiving a platinum-based chemotherapy agent at 0 - 4 days prior to Day 1 of Cycles 2, 3, 4, and 0 - 4 days prior to the last day of Cycle 4. Assess hearing impairment and tinnitus.
- ANCs must be obtained as follows:
 - The ANC must include both neutrophils and bands. The following equation is recommended:
$$\text{ANC} = \text{WBC} \times 1000 (\% \text{ Neutrophils} + \% \text{ Bands})$$
 - Obtain on Day 1 of Cycles 2, 3, 4 and at weekly visits

- Once ANC levels begin to decrease, ANC must be determined at least twice weekly (≤ 96 hours between blood collection) until ANC recovers to ≥ 500 cells/ μ L, then switch to weekly testing in the following situations:
 - If nadir is < 500 cells/ μ L, begin once ANC ≥ 500 cells/ μ L, OR
 - If nadir is ≥ 500 cells/ μ L, begin once ANC has increased by 50% above nadir

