6.4 Post-Treatment/Follow-up Assessments

All subjects will be followed for a minimum of 30 days after the last dose of protocol therapy (genistein/placebo) to assess for AEs. If subjects complete all four cycles of anti-neoplastic therapy, this visit will occur at 35 ± 5 days following the last day of Cycle 4. If subjects are withdrawn or discontinued prior to completion of the anti-neoplastic therapy, this will occur at 35 ± 5 days following the last day the study supplement is administered.

All serious adverse events (SAEs), other grade 3 – 4 AEs that are believed to be related to the investigational intervention, cancer progressions and relapses (including date, description, and sites), secondary malignancies (including date, description, and sites), and deaths (with date and clinical narrative) must be reported until 6 months after the end of the study intervention. See [Section 9.2](#) for additional information on AE and SAE reporting during this period.

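### No study chemistry is scheduled after Cycle 4 Day 1, so Cycle 4 is the only cycle without closing liver and kidney tests, and chemistry after two full genistein cycles is planned only in Arm A

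*Combined protocol and SAP*

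**What the plan says.** **Chemistry.** Table 3 marks the chemistry panel at pre-treatment, on Cycle 1 Day 1 and on Day 1 of Cycles 2 to 4. The Cycle 4 Last Day and Follow-up cells are blank. Footnote 11 reads "Chemistry labs to assess for general safety must be conducted on Day 1 of each cycle" and names creatinine, bilirubin, AST and ALT. Section 6.3 agrees: "Chemistry/metabolic liver function labs on Day 1 of each cycle".

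**CBC.** Section 6.3 has "CBC with differential on Day 1 of Cycles 2, 3, and 4, and at weekly visits". Footnote 12 to Table 3 is similar: "CBC must be collected once during Baseline (Day -7 to 1), and then Day 1 of Cycles 2, 3, and 4, and Day 8" of all four cycles. The Cycle 4 Last Day cell is blank. Section 6.3 adds ANC at least twice a week from the first fall until recovery, in every cycle.

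**Physical exam.** Footnote 10: "Full physical exam at the beginning of each cycle of chemotherapy, and a symptom-directed physical exam at each of the weekly treatment visits". The Cycle 4 Last Day cell is blank here too. Section 6.2.1, however, gives every visit other than pre-treatment and Day 1 a shorter exam guided by symptoms, which must look for endpoint conditions such as infection and mucositis.

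**What is scheduled on the last day of Cycle 4.** Blood is taken for CRP, ESR and homocysteine (footnote 13) and for the cytokine and isoflavone panels (footnote 14: "Blood sample must be drawn on Day 1 of Cycles 1, 2, 3, and 4, and the last day of Cycle 4"). An audiogram for platinum subjects, concomitant medication review, adverse event review, diary collection and supplement reconciliation are also due.

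**Afterwards.** Section 6.4 sets one adverse event visit: "this visit will occur at 35 ± 5 days following the last day of Cycle 4". Table 3 lists only adverse event review under Follow-up.

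**Purpose.** The synopsis states "Safety will be assessed by incidence and severity of AEs and changes in physical examinations". Its methodology paragraph says that laboratory tests and exams will be used to assess safety in each cycle.

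**The concern.** Footnote 6 to Table 3 equates a cycle's last day with Day 1 of the next. Chemistry on Day 1 of one cycle is therefore what shows the effect of the cycle before it. The study has no Cycle 5 Day 1, so Cycle 4 has no such reading unless one is added. The plan did add a closing measurement for the inflammatory markers, cytokines, isoflavones and hearing, but not for the safety panel.

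Under Section 4.7.2 the second supplement period ends on the last day of Cycle 4. In Arm B that period is genistein. No subject in Arm B therefore has a scheduled liver or kidney test after both genistein cycles. Section 1.3 calls pediatric safety data for soy isoflavones scant and makes safety a purpose of the trial. Under Section 9.1.4 an abnormal result can become an adverse event only if someone has measured it. A silent rise in creatinine or transaminases over Cycle 4 could go unrecorded.

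**Working it through.** The plan states no figure on this point, so the check is a count of scheduled draws.

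**Inputs**
- Chemistry days: Day 1 of Cycles 1, 2, 3 and 4 (Table 3, footnote 11, Section 6.3).
- Closing rule: the draw on Day 1 of cycle k+1 closes cycle k (footnote 6).
- Arm A: genistein in Cycles 1 and 2, placebo in Cycles 3 and 4. Arm B: the reverse (synopsis, Section 4.7.2).
- Planned subjects: 22 eligible per arm (Section 8.2), used only to scale the counts.

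**Cycles without closing chemistry.** Cycle 1 is closed on C2D1, Cycle 2 on C3D1 and Cycle 3 on C4D1. Cycle 4 is not closed. That is one cycle per subject: 44 of 44 × 4 = 176, or 44/176 = 25%.

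**End-of-cycle chemistry by arm and treatment, as written**

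| | Genistein cycles | Placebo cycles |
|---|---|---|
| Arm A, per subject | 2 (C2D1, C3D1) | 1 (C4D1) |
| Arm B, per subject | 1 (C4D1) | 2 (C2D1, C3D1) |
| Arm A, 22 subjects | 22 × 2 = 44 | 22 × 1 = 22 |
| Arm B, 22 subjects | 22 × 1 = 22 | 22 × 2 = 44 |
| Both arms | 44 + 22 = 66 | 22 + 44 = 66 |

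Full exams follow the same pattern of 2 against 1.

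**Draws after both genistein cycles.** In Arm A this is C3D1, which follows the 2-day washout of Section 4.7.2, for 22 subjects. In Arm B there is none: C4D1 follows one genistein cycle only.

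**Interval from the last scheduled test to the last day of Cycle 4**

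| | 14-day cycles (last day = Day 15) | 21-day cycles (last day = Day 22) |
|---|---|---|
| Chemistry (C4D1) | 15 − 1 = 14 days | 22 − 1 = 21 days |
| Last weekly CBC | 15 − 8 = 7 days | 22 − 15 = 7 days |

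The CBC row assumes that weekly visits fall strictly between Day 1 and the last day, as the blank Table 3 cell suggests. The symptom-directed exam has the same 7-day interval if the blank cell governs, and none if Section 6.2.1 governs.

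**With chemistry added on the last day of Cycle 4.** Each subject has 2 end-of-cycle draws in Cycles 1–2 and 2 in Cycles 3–4. Genistein draws become 44 in Arm A and 44 in Arm B, and pooled draws become 88 against 88.

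**Design figures.** None of this enters the power calculation. The stated power of about 80% reproduces (79.7% with continuity correction, 80.1% without; 20,000 simulated trials), and 44/0.90 rounds up to 49 subjects, as planned.

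**The case against.** The strongest reply is that Cycle 4 is far from unmonitored, and most of that reply stands. Adverse event review, and an audiogram for platinum subjects, take place on the last day. Section 6.2.1 calls for a symptom-directed exam at that visit. Weekly CBCs run through Cycle 4, with ANC at least twice a week from the first fall until recovery. Section 6.3 asks for the maximum grade of each target adverse event in every cycle. Section 9 has adverse events followed to resolution or stabilization.

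Three stronger readings that a reader might infer therefore fail:
- *Cycle 4 has no closing safety check.* The items above are closing checks. What is missing is chemistry, the full exam and a routine last-day CBC.
- *Mucositis and neuropathy durations are cut short in Cycle 4.* Section 6.2.1 supplies an exam aimed at endpoint conditions, and Section 9.1.1 requires dates of onset and resolution.
- *A late laboratory abnormality would be found only if symptomatic.* Section 9.1.4 lists four alternative criteria, and symptoms are only one. Subjects continuing chemotherapy may well have local tests around that day, and Section 6.3 expects standard-of-care assessments.

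A further reply is that each arm has two Day 1 chemistries within its own genistein cycles (C1D1 and C2D1 in Arm A, C3D1 and C4D1 in Arm B). That is true, but the first of each pair is a period-start baseline and says nothing about that period's supplement. It is also true that Section 8.4 specifies no analysis of chemistry values, so the consequence lies in detecting safety events and not in a planned test.

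What the reply does not answer is that no section schedules chemistry after Cycle 4 Day 1, or requires local results from that time as study data.

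**Conclusion.** The gap is real but narrow. Chemistry is not scheduled at the end of Cycle 4, so 25% of planned cycles have no closing liver and kidney tests. Chemistry after two full genistein cycles is planned in 22 of 44 subjects, all in Arm A. The last scheduled panel precedes the end of supplement by 14 or 21 days.

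A reader might infer that genistein is followed less closely than placebo. The counts do not support that. Arm A's placebo period has the same gap, and pooled end-of-cycle draws are 66 and 66. The imbalance is between periods. It matters for within-subject comparison of laboratory values, where Cycles 1–2 have two closing values and Cycles 3–4 have one, and for safety ascertainment at the end of Arm B's exposure.

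For the physical exam, only the full exam is clearly absent on the last day. The blank Table 3 cell and Section 6.2.1 disagree about the symptom-directed one.

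The conclusion assumes that Day 1 tests serve as the closing tests of the preceding cycle, as footnote 6 implies, and that all 44 subjects complete four cycles. Primary endpoint, power and sample size are unaffected. This is an inexpensive improvement and not a flaw in the main comparison.

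**What to change.** 1. In Table 3, footnotes 11 and 12 and Section 6.3, add the chemistry panel and a CBC with differential to Cycle 4 Last Day, taken at the blood draw already scheduled.
2. Mark the physical exam cell for that visit in Table 3, so that it agrees with Section 6.2.1.
3. State that these are the Cycle 4 closing safety values, and that they play the same part as the Day 1 values that close Cycles 1 to 3. Note that the Cycle 3 Day 1 values follow a 2-day washout, whereas these would be taken on the last day of supplement.

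The visit and venepuncture already take place, so no extra visit or procedure is needed. The downside is one extra routine panel for subjects whose chemotherapy ends at Cycle 4.

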6.2 Pre-treatment Assessments

Informed consent will be obtained from a parent or guardian of eligible minor subjects, or the patient if ≥ 18 years old. Oral assent will be obtained from minor subjects ≥ 7 years old, unless more stringent requirements are imposed by a site's IRB. Consent and assent must be obtained prior to any study-related procedures. ([Section 4.3](#), Procedure Manual)

Subject eligibility must be confirmed prior to subject enrollment using the inclusion and exclusion criteria ([Section 3.1](#) – [3.2](#)). The following data must also be collected pre-treatment:

- Clinical data: diagnosis, stage, grade, site(s) of disease
 - Stage (extent of spread): *in situ*, localized, regional, distant, unknown
 - Grade (differentiation level): well differentiated/low grade, moderately differentiated/moderate grade, poorly differentiated/high grade, undifferentiated/highest grade
- Anticipated anti-neoplastic treatment regimen for courses coinciding with this trial: therapeutic agents (i.e. chemotherapy, hormonal therapy, immunotherapy, other small molecule inhibitors, gene therapy), doses expressed per kilogram body weight, duration of cycle (14 or 21 days), radiation dose and number of fractions (if applicable)
- Demographic data: date of birth, sex, race, and ethnicity
- Blood sample collection for serum homocysteine, C-reactive protein (CRP), and erythrocyte sedimentation rate (ESR), and complete blood count (CBC) with differential must be drawn at baseline (Day -7 to Day 1). Raw data will be reported.
 - CBC with differential must include hemoglobin, hematocrit, platelet count, total white blood cell count and automated white blood cell differential (manual differential if automated not available) (Procedure Manual).
- Medical history and physical exam for the purpose of establishing baseline conditions ([Section 6.2.1](#))
- Audiogram on Day -7 to Day 1 for subjects receiving platinum-based chemotherapy
- Use of the following concomitant medications in the 28 days prior to the anticipated Cycle 1 Day 1: G-CSF, antimicrobials, blood product transfusions, anti-neoplastic agents, and soy-based products. See [Sections 4.8](#), [6.3](#), and the Procedure Manual for additional details on concomitant medications.

In addition, the following **target AEs** must be assessed during the Pre-treatment Period. Use assessment closest to Cycle 1 Day 1 if more than one assessment is done during the Pre-treatment period.

- Neutropenia
- Febrile neutropenia, with temperature
- Fever for temperatures > 101.5° F, or > 100° F more than once in a 24-hour period
- Infections and Infestations: Maximum grade for any AE listed in this CTCAE category. Infections meeting the AE reporting threshold must be listed in the medical history.
- Oral mucositis
- Tinnitus (subjects receiving platinum-based chemotherapy only)
- Hearing impairment (subjects receiving platinum-based chemotherapy only)
- Peripheral motor neuropathy (subjects receiving vincristine only)

